2.1.1 General definitions

All analyses will be based on assessments according to the investigator. This study will consist of the following epochs (refer to Figure 1-1):

- a pre-treatment period
 - from day of patient's study informed consent for this study to the day before first administration of study treatment within this study
- an on-treatment period
 - from day of first administration of study treatment within this study to 30 days after last administration of study treatment
- a follow-up period
 - starting at day 31 after last administration of study treatment within this study to the date of the last assessment collected in this study

Study treatment refers to:

- DFX FCT (Exiade[®])
 - The investigational open-label treatment will be provided as 90 mg, 180 mg, and 360 mg DFX FCT for oral use.
 - Treatment visits will occur at Visit 3 (Day 1), then every 2 weeks until Visit 5 (Month 1). Thereafter visits will be monthly until end of treatment (EOT) (Visit 28/Month 24).
 - The planned duration of study treatment in this study is for a maximum 24 months.

The date of first administration of study treatment within this study will be derived as the first date when a non-zero actual dose of study drug was administered as recorded on the Dosage Administration Record (DAR) Electronic Case Report Form (eCRF). The date of first administration of study drug within this study will also be referred to as 'start of study treatment'.

The date of last administration of study treatment is defined as the last date when a non-zero actual dose of study drug was administered as recorded on the DAR eCRF. This date will also be referred to as 'last date of study treatment'.

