2.5 Treatments (study treatment, rescue medication, concomitant therapies, compliance)

Unless otherwise stated, all analyses will be based on patients in the Safety Set.

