The prescribed count corresponds to the count prescribed by the investigator for the period that the patient should have taken the study treatment during this period. For each strength (90 mg, 180 mg, and 360 mg tablets), the prescribed count for a period is calculated from the daily prescribed count at the beginning of this period multiplied by the duration (days) of this period. The daily prescribed count is the sum of counts prescribed per strength. The duration of a period will be calculated using the following formula:

(end date of the period) - (start date of the period) + 1

The subsequent period duration calculation will exclude the start day (i.e., a day will be not be counted in subsequent periods). The total count prescribed is the sum of counts prescribed over all periods.

If a patient does not return the study drug, the compliance will not be calculated.

Descriptive statistics including 95% confidence interval (CI) for the mean relative consumed tablet count will be provided.

In addition, the persistence of DFX FCT will be summarised at Month 3, Month 6, Month 9, and Month 12. Persistence is defined as the continuous use of DFX FCT without a gap of \geq 30 or \geq 60 days over a fixed time interval of interest. A gap will be calculated as the time between two consecutive dates of study drug administration when study drug was administered (i.e. actual dose is non-zero) within the fixed time interval of interest.

Furthermore, a listing will be provided including dispensed/returned and prescribed counts as well as the relative consumed tablet count by center and patient number for the Safety Set.

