2.15 Interim analysis

There are no interim analyses in this study.

3 Sample size calculation

No formal sample size has been calculated. All patients enrolled into CICL670F2201 who have completed 24 weeks treatment will be offered participation in this current protocol and those consenting to participate will contribute to the pool of data.

According to enrolment of CICL670F2201 in Region Europe, a maximum of 90 patients should be eligible for enrollment in this study. However as only three countries (Austria, Greece, and Italy) are participating in this study which is less than originally foreseen, it is planned to enroll a maximum of 58 patients.

4 Change to protocol specified analyses

Due to insufficient patient numbers in the categories for the subgroups: age and main underlying disease, it was agreed to remove the planned age and main underlying disease subgroup analyses.

Within the protocol, it is stated that the Baseline serum ferritin value will be defined as the average of the 2 measurements obtained during the Screening period. It was clarified that this statement is in reference to the eligibility criteria and baseline serum ferritin should be derived for analysis purposes as outlined in Section 2.3.2.

5 Appendix

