5.1.4.2 Dose interruptions, dose delays, and dose changes

This section provides additional details to those included in Section 2.5.1.

Dose interruption

A dose interruption will be indicated in the eCRF by a dosing record with an actual total daily dose of 0 mg for one or more days. In order not to over count interruptions, dosing records with 0 mg entered as last dosing record will not be counted as interruptions. Those represent the reason for permanent discontinuation and will therefore be presented in the reason for treatment discontinuation analysis.

Dose reduction

A reduction is defined as a decrease from the previous non-zero dose. For example, in the sequence of planned dose (mg/kg/day) 25-0-15, the 15 mg/kg/day dose will be counted as a reduction. The planned zero dose is also counted as a dose reduction record. The reduction will be determined using the eCRF 'planned dose'. If the planned dose is reduced as described above, a reduction will be counted.

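### The SAP's persistence rule cannot register a permanent stop, so patients who stop for good without an earlier long gap count as persistent

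*SAP*

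**What the plan says.** SAP Section 2.5.1, under study compliance, states that "the persistence of DFX FCT will be summarised at Month 3, Month 6, Month 9, and Month 12". The concept comes first: "Persistence is defined as the continuous use of DFX FCT without a gap of" at least 30 or at least 60 days over a fixed interval. The calculation follows: "A gap will be calculated as the time between two consecutive dates of study drug administration when study drug was administered". Only days with a non-zero dose qualify, so both ends of a gap are days when drug was taken, and both must lie inside the interval.

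Three other parts of the SAP bear on this:

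- Section 2.1.1: "The date of last administration of study treatment is defined as the last date when a non-zero actual dose of study drug was administered". After that date there is no further dosing date that could close a gap.
- Section 5.1.4.2 does not count a final 0 mg record as an interruption. Of such records it says: "Those represent the reason for permanent discontinuation and will therefore be presented in the reason for treatment discontinuation analysis". It makes no link to persistence.
- Section 2.5 sets the population: "Unless otherwise stated, all analyses will be based on patients in the Safety Set". Nothing in 2.5.1 removes, censors or fails a patient who has discontinued.

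The protocol offers no fallback. Section 6.6.3.1 marks study drug compliance as not applicable, and Section 10.3 contains no persistence analysis.

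**The concern.** Persistence is meant to show how many patients keep taking the drug. The clearest failure is stopping and never restarting, and that is the one pattern the calculation cannot see. The concept (continuous use over a fixed interval) and the calculation (time between two doses) therefore disagree, and the calculation is what will be programmed.

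The rule also ranks patients the wrong way round: one who interrupts and resumes can fail, while one who never resumes passes. Convenience and compliance are part of the stated rationale for the new formulation (Protocol Sections 1.2.1 and 2.1), so an inflated persistence percentage could be read as evidence on a point that matters to the programme. Stopping is foreseeable in a study with up to 24 months of treatment.

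**Working it through.** The SAP states no persistence figure to reproduce, so the check applies the rule to constructed dosing histories and then sizes the error.

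**Inputs.** The thresholds (30 and 60 days), the time points and the gap rule come from SAP 2.5.1. Interval ends are Study Days 84, 168, 252 and 336, from Table 2-1, where a month is 4 weeks. Applying that month length to persistence is an assumption. With the planned days in Table 2-2 (85, 169, 253, 337), each off-drug period below is one day longer. Intervals are taken as running from Day 1, which the SAP does not state; the other reading is covered below. The number of patients is 58 (SAP Section 3: "it is planned to enroll a maximum of 58 patients").

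**Two patients, 30-day threshold.**

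- Patient A doses daily to Day 40 and never resumes. The largest between-dose gap is 1 day, so A is persistent at all four time points. Time off drug that is not measured: 84 − 40 = 44, 168 − 40 = 128, 252 − 40 = 212 and 336 − 40 = 296 days.
- Patient B doses daily to Day 40, resumes on Day 80 and continues. The gap is 80 − 40 = 40 days, so B is non-persistent at all four time points.

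Other stop days behave like A: daily dosing ending on Day 20, 60, 80 or 150 gives a largest gap of 1 day at every time point, under both thresholds. A patient with a single dose on Day 1 has no gap at all and also passes throughout.

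**Separate quarters instead of cumulative intervals.** B then fails only at Month 3. A has no dosing dates in the later quarters, hence no gap, and still never fails.

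**An interruption open at the interval end.** A patient who stops on Day 40 and resumes on Day 100 has no gap by Day 84, so passes at Month 3 despite 44 days off drug. The gap of 100 − 40 = 60 days appears only from Month 6.

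**Size of the error.** Let d be the share of patients whose last dose falls at least 30 (or 60) days before the time point, g the share of the other patients with an earlier qualifying gap, and gs that share among the stoppers.

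- Corrected persistence = (1 − d)(1 − g)
- Rule as written = (1 − d)(1 − g) + d(1 − gs)
- Overstatement = d(1 − gs)

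The documents give none of d, g or gs, so all three are assumptions.

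| g | d | Corrected | As written, gs = g | As written, gs = 0 | Overstatement (points) |
|---|---|---|---|---|---|
| 5% | 10% | 85.5% | 95.0% | 95.5% | 9.5 to 10 |
| 5% | 20% | 76.0% | 95.0% | 96.0% | 19 to 20 |
| 5% | 30% | 66.5% | 95.0% | 96.5% | 28.5 to 30 |
| 5% | 40% | 57.0% | 95.0% | 97.0% | 38 to 40 |
| 10% | 10% | 81.0% | 90.0% | 91.0% | 9 to 10 |
| 10% | 20% | 72.0% | 90.0% | 92.0% | 18 to 20 |
| 10% | 30% | 63.0% | 90.0% | 93.0% | 27 to 30 |
| 10% | 40% | 54.0% | 90.0% | 94.0% | 36 to 40 |

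When gs = g, the reported figure is 1 − g whatever the stop rate: it carries no information about stopping. In patients, for d = 20% and g = 5%: 58 × 0.19 = 11.0 and 58 × 0.20 = 11.6 misclassified. If half of the stoppers had an earlier gap (gs = 0.5), the overstatement falls to d/2, which is 10 points at d = 20%. For a given threshold, d rises from Month 3 to Month 12, and it is lower for 60 days than for 30.

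**The case against.** The best reply is that the first sentence already asks for continuous use over the interval. A programmer who takes it seriously would fail Patient A, so the SAP may be unclear without being wrong. It is true that the intent can be read this way. But the SAP then states how a gap is calculated, and that is the only operational test it gives. A result that is right only if the programmer overrides the written calculation is not properly specified.

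A second reply concerns the denominator. SAP Section 2.1 bases percentages for categorical variables on non-missing data, so a stopped patient might have no persistence value at a later month. The SAP does not say this, and the dosing dates of such a patient are known, not missing. It would not help either: dropping stoppers gives (1 − d)(1 − g)/(1 − d) = 1 − g, for example 0.76/0.80 = 95.0%, the same inflated figure as gs = g.

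Third, the stakes are limited. Persistence is in no objective or endpoint. Exposure categories in the same section have boundaries at 12, 24, 36 and 48 weeks, and disposition and reasons for discontinuation are tabulated, so a careful reader could see how many stopped. This stands and limits the severity, but none of these tables corrects the persistence percentage.

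Finally, nothing in the documents supports a particular stop rate, and entrants had already completed 24 weeks in the preceding study. That also stands: with few stops the error is small.

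**Conclusion.** The rule is wrong as written. It never measures the time from the last dose to the end of the interval, so a patient who stops for good without an earlier qualifying gap cannot become non-persistent. Compared with a rule that counts this time, it can overstate persistence but never understate it. That conclusion does not depend on the month length or on whether intervals are cumulative or quarterly.

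The overstatement is d(1 − gs). Under the illustrative values d = 20% and g = 5%, it is 19 to 20 percentage points, or 11 to 12 of 58 patients; the actual size depends on stop rates the documents do not give. The damage is confined to a supportive summary. The correction should be made, but it does not touch the primary safety analysis or the ferritin analysis.

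**What to change.** Add to SAP Section 2.5.1 that the time from the last non-zero dose to the end of the interval also counts as a gap, obtained by the same subtraction of dates and held to the same 30- and 60-day thresholds. This covers permanent stops and interruptions still open at the interval end. A stop less than 30 (or 60) days before a time point would still count as persistent there, in line with the threshold.

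The same edit should state that each interval runs from Day 1 to Month 3, 6, 9 or 12, give the month length, and confirm that all Safety Set patients stay in the denominator. Because the rule treats every stop alike, including death, pregnancy and administrative reasons, a cross-reference to the discontinuation-reason table would help the reader.

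The cost is one or two sentences and a small program change using dates already on the Dosage Administration Record eCRF. SAP Amendment 1 was itself issued before database lock and edited this section. The reported figure will be less favourable.

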2.5.2 Prior and concomitant therapies

The number and percentage of patients taking prior and concomitant therapies will be summarized for the Safety Set.

Summaries will be presented separately for prior and/or concomitant medications. Concomitant therapies will include medications and significant non-drug therapies taken between the first and last day with study medication + 30 days, excluding medications that start on the last day of study medication. Prior therapies will include medications or significant non-drug therapies starting and ending prior to the start of study treatment in this study. Medications starting prior to the start of study treatment in this study and continuing after the start of study treatment will be counted in both summaries.

Prior or concomitant medication will be identified based on recorded or imputed start dates of medication taken in this study. The rules for imputing incomplete start dates are described in Section 5.1.2.

Medications will be identified by Anatomical Therapeutic Chemical (ATC) class and PT according to the World Health Organization (WHO) Drug Reference List dictionary (201603 or a more recent version). Tables will show the overall frequency and percentage of patients receiving at least one dose of the therapy.

A listing of prior and concomitant therapies will be provided by center and patient number for the Safety Set.

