6.4.3 Prohibited concomitant therapy

Prohibited concomitant therapy includes:

- Aluminium containing antacid therapies.
- Concomitant use of deferasirox with potent UDP-glucuronosyltransferase (UGT) inducers (e.g. rifampicin, phenytoin, phenobarbital, ritonavir) or cholestyramine.
- Any ICT other than the study drug.
- Any investigational drug other than study medication.

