7.1.6 Follow-up for safety evaluations

All patients must have safety evaluations for 30 days after the last dose of study treatment.

Data collected should be added to the AE eCRF and the Concomitant Medications eCRF.

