10.3 Treatments (study treatment, concomitant therapies, compliance)

The following variables will be summarized with descriptive measures for the Safety Set: duration of exposure (at intervals as described in the Statistical Analysis Plan); average planned (mg/kg/day) and average actual daily dose (mg/day); cumulative planned (mg/kg) and total actual dose (mg); percentage of planned dose taken; frequency of interruptions,

decreases and increases in planned dose overall and by reason for change as recorded in the eCRF.

The total patient-years while on treatment, calculated as the sum of (overall drug exposure)/365.25 will be provided.

The duration of exposure is defined as the number of weeks between the start and end of study medication. The end of study medication day is the last day with a non-zero actual dose of study medication as recorded on the drug administration pages.

The average daily dose (planned or actual) is calculated as the mean dose over all days between first and last dose, including interim days with zero dose (interruptions). The cumulative dose is calculated as the sum over the daily doses of all days between first and last dose. The current weight is used when calculating the actual daily dose.

The percentage of planned dose taken is derived as $100 \times \text{cumulative}$ actual dose (mg)/cumulative planned dose (mg/kg).

Prior and concomitant medications and significant non-drug therapies will be summarized using frequency tables according to WHO Anatomical Therapeutic and Chemical class and WHO generic term. Prior medications are defined as drugs taken prior to the first dose of study medication. Concomitant medications are medications taken between the first and last day with study medication, excluding medications started on the last day of study medication. Medications which start prior to the first dose of study medication and continue thereafter are counted in both summaries.

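### SAP 2.5.2 extends the concomitant-therapy window to 30 days after the last dose but still excludes therapies started on the last dosing day, leaving a one-day gap and mixing post-treatment with co-administered drugs

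*SAP*

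**What the plan says.** Protocol 10.3 sets the rule as follows: "Concomitant medications are medications taken between the first and last day with study medication, excluding medications started on the last day of study medication". SAP 2.5.2 widens it to therapies "taken between the first and last day with study medication + 30 days, excluding medications that start on the last day of study medication".

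The same SAP paragraph defines the other category: "Prior therapies will include medications or significant non-drug therapies starting and ending prior to the start of study treatment in this study". It adds that therapies begun before the first dose and "continuing after the start of study treatment will be counted in both summaries".

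Four other provisions bear on the point:

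- **Last dosing day.** SAP 2.1.1 fixes its meaning: "The date of last administration of study treatment is defined as the last date when a non-zero actual dose of study drug was administered".
- **On-treatment period.** SAP 2.1.1 runs it "from day of first administration of study treatment within this study to 30 days after last administration of study treatment", and SAP 2.6.1 uses the same 30-day limit for treatment-emergent adverse events.
- **Prohibited therapy.** Protocol 6.4.3 includes "Any ICT other than the study drug".
- **Data after the last dose.** For the 30-day safety follow-up, Protocol 7.1.6 states: "Data collected should be added to the AE eCRF and the Concomitant Medications eCRF".

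SAP Section 4, which lists changes to the protocol-specified analyses, names the dropped age and underlying-disease subgroups and the baseline ferritin definition. It does not mention the concomitant-therapy window.

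**The concern.** In the protocol the exclusion has a clear purpose. The window closes on the last dosing day, and a drug begun that day is treated as belonging to the period after treatment. Once the window is pushed out by 30 days, that purpose is gone. The SAP then rejects a drug begun on the last dosing day and accepts one begun the day after.

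Two kinds of record end up in the wrong place. A drug given for an adverse event that starts on the last dosing day drops out of both medication summaries, although the event itself is treatment-emergent. A chelator begun after study drug has ended is labelled concomitant with it, and nothing in SAP 2.5.2 separates it from a chelator taken during dosing. In a single-arm study whose primary objective is safety, readers use the medication table to look for other explanations of adverse events and laboratory changes. The table should therefore say plainly what was taken alongside study drug and what came afterwards.

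**Working it through.** The plan gives no figure to reproduce, so the check applies each rule literally.

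**Notation.** F is the first dosing day and L the last day with a non-zero dose (SAP 2.1.1). A therapy starts on day s and ends on day e.

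**Rules.**

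- Protocol 10.3, concomitant: s ≤ L, e ≥ F and s ≠ L.
- SAP 2.5.2, concomitant: s ≤ L+30, e ≥ F and s ≠ L.
- SAP 2.5.2, prior: s < F, whether the therapy ends before F or continues past it.
- SAP window with the exclusion deleted: s ≤ L+30 and e ≥ F.

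**Illustration.** Take F = 1 and L = 673, the planned Month 24 day in SAP Table 2-2, and let each therapy last long enough that e ≥ F. These values are assumptions; the pattern by start day does not depend on them.

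| Start day | Protocol: concomitant | SAP: concomitant | SAP: prior | SAP with exclusion deleted |
|---|---|---|---|---|
| L−1 (672) | yes | yes | no | yes |
| L (673) | no | **no** | **no** | yes |
| L+1 (674) | no | yes | no | yes |
| L+30 (703) | no | yes | no | yes |
| L+31 (704) | no | no | no | no |

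**Results.**

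1. The SAP adds the start days L+1 to L+30 to the protocol's rule: 703 − 674 + 1 = 30 days.
2. Exactly one start day inside the SAP window is rejected, namely L.
3. A start on L is never prior, because prior requires s < F and L cannot be earlier than F. It is therefore in neither summary. Since the SAP listing covers prior and concomitant therapies, a literal reading leaves it out there too.
4. An adverse event with onset on L falls within F to L+30 and is treatment-emergent, but a drug begun for it on L is not concomitant.
5. A chelator begun on any day from L+1 to L+30 is concomitant under the SAP, although its use never overlapped with study drug. One begun on L itself is not counted.

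The exclusion cannot be read as referring to day L+30. Its wording points to the last day of study medication, which SAP 2.1.1 ties to the last non-zero dose.

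**The case against.** Much can be said for the plan.

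- **The 30-day extension is sound.** It matches the on-treatment period and the window for treatment-emergent events. That stands, and the extension should be kept.
- **The SAP captures more than the protocol.** Starts on L are lost under Protocol 10.3 as well, along with everything begun later. This is true, but the protocol's rule is consistent with its own window, and the SAP's is not.
- **Treated events stay visible elsewhere.** SAP 2.9.1 summarises events requiring additional therapy and events leading to discontinuation, and Protocol 8.1.1 records on the adverse event form whether medication was given. A reader might infer that treatments begun on L disappear from the trial. They do not: the records remain in the database, and what is lost is the drug's entry in the medication summaries and perhaps the listing. If study drug is stopped on the day after the last dose, a treatment begun on that later day is counted.
- **Prohibited medication has its own output.** SAP 2.2 tabulates deviations for excluded concomitant medication. A reader might infer that the medication table would show widespread prohibited chelation, or that the share of patients could swing from none to all with a one-day shift in start dates. The documents give no rate of replacement chelation within 30 days. The 58 patients in SAP Section 3 are a planned maximum, not a number treated. Capture after the last dose is also uncertain: Protocol 7.1.6 directs the data to the medication form, but the medication row of Table 7-1 has no mark at the 30-day follow-up.
- **The prior-therapy wording.** A reader might see a contradiction between requiring therapies to end before the first dose and counting continuing ones in both summaries. The second statement settles how continuing therapies are counted and gives the protocol's result, so no count changes.
- **Disclosure.** The SAP document history reports a clarified definition, prompted by a mismatch with the table shells. That is not a declaration of a change from Protocol 10.3. The shells are not available, so any split they make cannot be judged.

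**Conclusion.** The rule is wrong as written, and the matter is minor. By start day, the defect is one missing day (L) followed by 30 days (L+1 to L+30) in which therapies begun after treatment are pooled with those taken during it. The number of patients or drugs affected cannot be derived from the documents.

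The conclusion rests on a literal reading of SAP 2.5.2 and on the SAP's own definition of the last dose. A programmer might list every record or split the table regardless, but the text does not require it. The effect stops at descriptive medication output. The adverse event and laboratory summaries for the primary objective and the ferritin summaries do not use this definition, and no hypothesis is tested.

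**What to change.** 1. In SAP 2.5.2, keep the window to 30 days after the last dose and delete the clause excluding therapies that start on the last dosing day. This closes the gap at L and keeps the table aligned with the treatment-emergent period.
2. In the concomitant table, show therapies started on L+1 to L+30 separately from those taken during dosing, so that a chelator begun after treatment is not read as co-administered.
3. In SAP Section 4, list the wider window as a departure from Protocol 10.3.

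Going back to the protocol's window would also close the gap, but it would break the match with the on-treatment period, so it is not the better repair. No new data are needed. The cost is a few words in the SAP and a small amount of extra table programming.
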